# 7.1.2 Responsibilities of ICR-CTSU

ICR-CTSU has responsibility for storing the clinical trial data and undertaking and reporting interim and final analyses.

#### 7.2 Case Report Forms (CRFs)

A series of questionnaires will be completed by both the patient and research team at set time points during the study in order to assess the patient's late radiotherapy side effects and quality of life. The CRFs completed in clinic should be signed and dated and forwarded to the Trial Coordinator once completed. The Trial Coordinator will review incoming CRFs for compliance with the protocol, and for inconsistent or missing data. Should any missing data or data anomalies be found, queries will be sent to the relevant Royal Marsden staff for resolution. Following initial review, the Trial Coordinator will enter the CRF data items into the clinical study database held at ICR-CTSU.

The CRFs will not be made available to people outside of the research team, however, access will be granted for audit and monitoring purposes and will be provided to regulatory authorities, Research Ethics Committee or other relevant ICR or Trust personnel.

#### 7.3 **Protocol compliance**

This trial is being conducted in accordance with applicable statutory and regulatory requirements and guidelines for non-commercial research in the NHS under the EU Clinical Trials Directive.

#### 7.4 Treatment compliance/deviation

It is the responsibility of appropriate Royal Marsden site staff to complete a Treatment Compliance Form for each patient who is randomised to the trial.

If the patient does not receive their treatment as per the trial protocol, the Royal Marsden site staff must also complete a Deviation Form.

If a patient's condition deteriorates during Tocovid SupraBio+PTX therapy, and their GP requires them to be hospitalised for investigations and treatment, they can be temporarily removed from the trial. Tocovid SupraBio+PTX therapy in accordance with their original randomisation will be resumed on completion of the referral, unless the GP decides against this in liaison with the CI. A copy of the Deviation Form as well as Treatment Compliance Form must be completed for such patients.

All completed forms should be signed and sent via hard copy or email to the CI, [name], Consultant in Clinical Oncology, The Royal Marsden, [name]. [contact]. Email: [contact]

#### 7.5 Treatment withdrawal

Patients must be withdrawn from the study for the following reasons:

- Disease progression before completion of study treatment\*. •
- Withdrawal of consent for treatment and/or study participation.

- Unacceptable treatment related toxicity or adverse events as judged by either the patient's GP or the Chief Investigator.
- Pregnancy.
- Patient non-compliance.
- Death.

\*If a patient satisfies the criteria for treatment withdrawal based on disease progression but is deemed by the Chief Investigator (CI) to be benefitting from treatment (e.g., symptomatic relief), such a patient may remain on the trial (i.e., continue receiving IMP and undergoing trial assessments) until such a time when the CI determines it no longer beneficial to do so.

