#### 5.4.2 Monitoring of patients during treatment

- i) Adverse events will be recorded and reported as appropriate.
- ii) Any patient can be withdrawn from the study at any time.
- iii) Reasons for withdrawals and any adverse events will be documented and considered in the analysis.
- iv) Patients will be asked to produce a list of current medication (including dosage) before they enter into the study and to keep a medication diary during their Tocovid SupraBio + PTX/placebo therapy. Changes in medication during the 12

15

months of follow up will be collected at the assessment 24 months post randomisation.

- v) Levels of plasma GT3 will be measured at baseline, 3, 6, 9 and 12 months to confirm compliance with drug in those randomised to Tocovid SupraBio/PTX and undetectable levels of GT3 in those allocated placebo. Appropriate Royal Marsden site staff will check compliance in clinic from diary card kept by patients and any leftover trial medication (if applicable).
- 5.5 Follow up assessments during and after treatment (please see table below)
  - Patient self-assessments using IBDQ, the EORTC Quality of Life Questionnaires (QLQ-C30 & QLQ-CR29) and the Gastrointestinal Symptom Rating Scale 3, 6, 9, 12, 18 and 24 months after randomisation.
  - ii) Physician/Clinical Nurse Practitioner grading of late radiation-induced side effects using the modified CTCAE Version 4 form 3, 6, 9, 12 and 24 months after randomisation.
  - iii) Re-assessment with a 7-day food diary at 6 months and 1 year.
  - iv) Flexible sigmoidoscopy with rectal biopsies (optional) and medical photographs of rectal mucosa 12 and 24 months after randomisation.
  - v) Blood levels of IL6, TGF beta and MMP9 3, 6, 9, 12 and 24 months after randomisation as markers of fibrosis.

Procedure	Follow up (months post-randomisation)						
	3	6	9	12	18	24	
Patient self-assessment questionnaires	$\checkmark$	$\checkmark$	$\checkmark$	$\checkmark$	$\checkmark$		
CTCAE Version 4 grading	$\checkmark$	$\checkmark$	$\checkmark$	$\checkmark$		$\checkmark$	
Clinical assessments	$\checkmark$	$\checkmark$	$\checkmark$	$\checkmark$		$\checkmark$	
7 day food diary		$\checkmark$		$\checkmark$			
Rectal photographs				$\checkmark$		$\checkmark$	
Rectal biopsies (optional)						$\checkmark$	
Blood sample	$\checkmark$		$\checkmark$			$\checkmark$	

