#### 6.4 Analysis

#### Primary endpoint

Analysis of the bowel function component of the Modified Inflammatory Bowel Disease questionnaire is the primary endpoint, and analysis will be carried out on an intention to treat basis. The mean difference in change from baseline to 12 months in both trial arms will be compared using the Mann-Whitney U test, or unpaired t-test if the values are approximately normally distributed. If necessary, multivariate analysis will be used to adjust for any potential confounding factors, though the ability to use multivariate analysis will be limited by the fact there are only 33 patients in one arm. The impact of missing values will be investigated by using techniques such as LOCF.

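### Section 7.5 withdraws patients from the study, not only from treatment, which taken literally conflicts with the intention-to-treat analysis of 12-month IBDQ-B

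*Protocol*

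**What the plan says.** Four places in the protocol bear on this.

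- **Section 7.5 (Treatment withdrawal).** The heading concerns treatment, but the rule is mandatory and concerns the study: "Patients must be withdrawn from the study for the following reasons". The list includes "Patient non-compliance" and "Unacceptable treatment related toxicity or adverse events as judged by either the patient's GP or the Chief Investigator". It also includes withdrawn consent, whether for treatment, for participation or for both, so a patient who declines only the capsules falls under it.
- **Footnote to section 7.5.** For a patient with disease progression who is thought to be benefiting, "such a patient may remain on the trial (i.e., continue receiving IMP and undergoing trial assessments". Treatment and assessment are named together as what staying on the trial means.
- **Section 7.4 (Treatment compliance/deviation).** If a patient deteriorates and the GP requires hospital admission, "they can be temporarily removed from the trial". Treatment then resumes by default. The section does not say whether questionnaires continue meanwhile.
- **Section 6.4 (Analysis, primary endpoint).** For the change in IBDQ-B from baseline to 12 months, "analysis will be carried out on an intention to treat basis". The impact of missing values is to be explored with methods such as LOCF.

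No section says that a patient who stops treatment early still completes the 12-month IBDQ.

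**The concern.** An intention-to-treat comparison needs the 12-month outcome from patients whether or not they stayed on their capsules. If leaving treatment also means leaving the study, the patients without a 12-month score are those who could not tolerate the treatment, did not take it or no longer wanted it. What is then observed is a comparison of those who stayed. Carrying an earlier on-treatment score forward fills the gap in the data set but does not supply the 12-month outcome.

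A statistical analysis plan can choose among missing-data methods, but it cannot bring back questionnaires that were never sent. The matter therefore belongs in the protocol.

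**Working it through.** **The plan's own figures.** With a difference of 7.5, SD 10, two-sided alpha 1.67% and 2:1 allocation (section 6.3), a t-test with 66:33 patients has 85.8% power. With 64:32 it has 84.6%, so 99 is the smallest 2:1 total that reaches 85%. Allowing for drop-out, 99/(1 − 0.15) = 116.5, rounded up to 117. Both stated figures reproduce, so the problem is not the sample size. Recruitment of 117 at 2:1 is 78 active and 39 placebo. Section 6.4 nevertheless speaks of 33 patients in one arm, in the same paragraph as the intention-to-treat promise. That is the count left after drop-out.

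**Bias formula.** Let m be the share of an arm with no 12-month score. Let g be the mean change of those lost minus the mean change of those observed. The mean over all randomised patients in an arm is the observed mean plus m × g, so

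bias = observed difference − all-randomised difference = −(m_A × g_A − m_P × g_P),

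where A is active and P is placebo. Positive values favour the active arm.

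**Inputs.** The documents give only the overall 15% drop-out, which is 117 − 99 = 18 patients. They give no loss by arm and no outcome for those lost. Every m and g below is therefore an assumption.

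| Assumed loss, active / placebo | g, active / placebo | Calculation | Bias (points) |
|---|---|---|---|
| 15% / 15% | −5 / −5 | −(−0.75 + 0.75) | 0 |
| 20% / 5% | −5 / −5 | −(−1.0 + 0.25) | +0.75 |
| 15/78 / 3/39 | −10 / −10 | (0.192 − 0.077) × 10 | +1.15 |
| 20% / 5% | −10 / −10 | −(−2.0 + 0.5) | +1.5 |
| 15% / 15% | −10 / 0 | −(−1.5 − 0) | +1.5 |
| 20% / 5% | −10 / 0 | −(−2.0 − 0) | +2.0 |
| 5% / 25% | −10 / −10 | −(−0.5 + 2.5) | −2.0 |

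Against the target, 1.15/7.5 = 15% and 2.0/7.5 = 27%. The last row has 11.7% loss overall; the others have 15%.

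**Effect on the test.** Take a true all-randomised difference of zero, SD 10 and the patient numbers that each scenario leaves. The nominal two-sided 1.67% error rate then becomes about 2.4% at a bias of +0.75, 4.7% to 4.8% at +1.5, and 7.7% at +2.0. It stays at 1.67% when the bias is zero.

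**Effect of full follow-up on power.** With all 117 observed, power for 7.5 points is 91.7%. If 10%, 15% or 20% of the active arm stop and lose all benefit (assumption), the all-randomised difference is 6.75, 6.375 or 6.0 and power is 84%, 79% or 73%. Full follow-up guards against bias. It does not guarantee more power.

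**The case against.** The best reply is that section 7.5 is loosely worded and means treatment only. Its heading says so, and the footnote speaks of criteria for treatment withdrawal and covers progression alone. Section 5.5 schedules questionnaires at 18 and 24 months, after the 12-month course has ended, so assessments are not in general tied to receiving IMP. Section 7.4 asks for a Deviation Form when treatment departs from the protocol, and section 6.5 plans a safety analysis by treatment received. Both suggest that patients who deviate may stay in. This shows that the end of outcome collection is not stated outright. It does not remove the conflict, because the operative sentence says study, consent withdrawn for treatment alone is enough to trigger it, and nothing provides otherwise.

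Three stronger readings may tempt a reader, and the documents do not support them.

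- **That deterioration ends follow-up.** Removal under section 7.4 is optional, temporary and limited to patients who are to be hospitalised.
- **That plasma GT3 testing exposes non-compliance in the active arm only and so drives unequal withdrawal.** Sections 5.4.2 and 5.8.2 also use diary cards, leftover medication and returned packaging, which work in both arms. No passage says that GT3 results reach clinic staff during treatment.
- **That an intention-to-treat analysis cannot be done.** All randomised patients can be analysed as allocated under stated missing-data assumptions, and section 5.4.2 says that reasons for withdrawal will be considered in the analysis. What would be lacking is observed 12-month data for everyone.

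**Conclusion.** The point holds as a conflict of wording with a real consequence. Read literally, section 7.5 ends outcome collection for patients whose data the intention-to-treat analysis in section 6.4 needs, and LOCF does not replace those data.

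Whether this biases the result, and in which direction, is not documented. Unequal loss is plausible: section 5.9.3 lists diarrhoea, bleeding and gastrointestinal problems for pentoxifylline, which overlap with the outcome. The same section gives their frequency as unknown and describes the drug as well tolerated overall. A reader might infer that the active arm must be favoured, but patients leaving placebo for lack of improvement would push the other way.

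The bias is zero with equal loss and equal prognosis. It is about 1.2 points, or 15% of the target, under the 15/78 versus 3/39 assumption with a 10-point gap, and up to about 2 points in either direction under the more extreme assumptions shown. The 1.2-point figure attributes all 18 planned drop-outs to this rule. Some of them may be deaths or withdrawals from follow-up, which no change of wording would recover.

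**What to change.** Reconcile sections 6.4, 7.4 and 7.5 so that stopping treatment is separate from ending outcome collection.

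- In 7.5, change withdrawal from the study to withdrawal from study treatment, and leave the listed reasons as they are.
- State that the IBDQ and the other questionnaires continue on schedule to 12 and 24 months unless the patient withdraws consent to follow-up or dies.
- In 7.4, state that a temporary interruption of treatment does not interrupt the questionnaires.

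This is an amendment of wording, with the recruitment target unchanged at 117. Section 8.3 already collects addresses for sending questionnaires, and off-treatment questionnaires are already scheduled at 18 and 24 months. The downside is some extra postage and chasing.

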#### 7.6 Direct Access to Source Data

On a day to day basis only members of the research team will have direct access to data and documents pertaining to this study. Access for audit purposes will be provided to regulatory authorities, Research Ethics Committee or other relevant ICR or Trust personnel.

The Case Report Form will be considered source data for this study as the forms are questionnaires completed directly by patients and/or clinical staff. Thus the information will not be recorded in the medical notes or on the Hospital Information System. However, consent and eligibility should be documented in the medical notes and this will be checked at random as part of the monitoring for this study.

Key eligibility components to be recorded on the Royal Marsden Electronic Patient Record System.

#### 7.7 Trial Management

#### 7.7.1 Trial Management Group

A Trial Management Group (TMG) will be set up and will include the Chief Investigator, Co-investigators and identified Collaborators, the Trial Statistician, Clinical Nurse Practitioner and the Trial Co-ordinator. Key study personnel will be invited to join the TMG as appropriate to ensure representation from a range of professional groups. Notwithstanding the legal obligations of the Sponsor and Chief Investigator, the TMG have operational responsibility for the conduct of the trial.

#### 7.7.2 Trial Steering Committee

A Trial Steering Committee (TSC) will monitor and supervise the progress of the trial. The role of the TSC is to provide overall supervision of the trial on behalf of the funding body. In particular, the TSC will concentrate on the progress of the trial, adherence to the protocol, patient safety and the consideration of new information. Day-to-day management of the trial is the responsibility of the Chief Investigator and TMG.

Membership will be limited and include an independent Chair (not involved directly in the trial other than as a member of the TSC), not less than two other independent members, the Chief Investigator and the Trial Statistician.

The Trial co-ordinator and other key members of the TMG will attend meetings (as observers) as appropriate. Observers from the funding body and, if applicable, host Institutions or sponsors will be invited to all meetings. The TSC will meet at least annually.

# 7.7.3 Independent Data Monitoring Committee

An Independent Data Monitoring Committee (IDMC) will be established to oversee the safety and interim efficacy of the trial. This committee will be constituted according to MRC Good Clinical Practice (MRC GCP). The IDMC will meet on a regular basis as they see fit, but no less than annually. Following each meeting, the IDMC will report their findings and recommendations to the TSC and to the TMG.

Interim analysis (split by treatment group) of IBDQ, modified CTCAE Version 4 grading, EORTC QLQ-C30 and 38, side-effects, tolerability and other endpoints for all randomised patients will be supplied in strict confidence by the trial statisticians to the IDMC together with any other analyses that the IDMC may request. The complete IDMC reports will remain confidential to the IDMC members and statisticians providing the report, however the Chief Investigator and Trial Co-ordinator will receive subsets of the report as seen fit by the IDMC (e.g. accrual, compliance and data completeness). Basic accrual data and safety reports, aggregated across the two treatment groups will be produced at appropriate periodic intervals and distributed to the TMG.

The main criterion for early stopping of the trial by IDMC will be that evidence from the trial or from other sources supplies a) proof beyond reasonable doubt that for all, or for some types of patient, one treatment regimen is clearly indicated or contraindicated in terms of a net difference in therapeutic effect or b) evidence that might reasonably be expected to influence routine clinical practice. Criteria for the above will usually be a difference in CTCAE Version 4 significant at p<0.001.

No results will be made available to participants or the sponsor until the IDMC consider the results to be clinically and statistically informative. The IDMC may recommend continuation beyond the planned number of patients in the trial if it is felt that further information is required to address reliably the hypothesis in question.

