Physician assessments appear to under-report morbidity. For example, the frequency and severity of gastrointestinal toxicity 18 months post-radiotherapy in a series of prostate radiotherapy trials was 29-45% grade 1, 5-14% grade 2, 0.6-3% grade 3 and 0-1% grade 4 (32-37). However, toxicity was a secondary endpoint and was measured using crude Radiation Therapy Oncology Group (RTOG) external assessments (20, 38-39). A rather different and more sobering picture is obtained from retrospective studies based on patient self-reporting. These studies reveal that patients often do not report toxicity for a variety of reasons (15), and that new bowel symptoms are common and have the greatest impact on quality of life (40). These studies suggest that at least 30% of bladder and gynaecological patients and 20% of all patients treated for prostate cancer have 'gastrointestinal symptoms causing moderate or severe distress' as a result of their radiotherapy (41-44). Two other studies using questionnaires proposed for use in the PPALM study found that 50% patients are left with long-term chronic gastrointestinal side effects interfering with daily activity (39, 45). Results in the rectal patients were similar to those described in an earlier detailed case controlled study (46).

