#### 6.2 **Principal Endpoint**

#### 6.2.1 Primary endpoint

Change at 12 months in the bowel disease subset of the Modified IBDQ Quality of Life questionnaire.

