#### Secondary Endpoints

The proportions of patients showing a change in rectal IBDQ bleeding score and Faecal incontinence score will be compared using Fisher's exact test.

There will be no formal statistical analysis of the other secondary endpoints but the descriptive nature of these results will be used to strengthen the interpretation of changes in the primary endpoint. Several analyses will be carried out including but not limited to the following:

- i) Changes in modified CTCAE Version 4 grades.
- ii) Standard procedures will be followed for describing quantitative changes in QoL domains using EORTC Quality of Life Questionnaires (QLQ-C30 and CR29).
- iii) Photographs of rectal mucosa will be scored by two experienced endoscopists, who will be blinded with respect to treatment allocation and time of assessment (pre- or post-treatment). The mucosal appearance will be scored using the Wachter classification (51). Disagreement in any scores will be resolved by arbitration after discussion with a third independent endoscopist. Differences in the appearance before and after treatment between the two groups will be assessed.
- iv) Change in levels of 3 serum markers of fibrosis.

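### The only numerical guide for IDMC early stopping names CTCAE, a descriptive secondary outcome, and not IBDQ-B, the endpoint the trial is powered on

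*Protocol*

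**What the plan says.** The relevant statements are all in the Protocol.

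- **Remit (7.7.3).** "An Independent Data Monitoring Committee (IDMC) will be established to oversee the safety and interim efficacy of the trial". The data it receives include "Interim analysis (split by treatment group) of IBDQ, modified CTCAE Version 4 grading", along with other endpoints and any analysis it asks for. On timing, "The IDMC will meet on a regular basis as they see fit, but no less than annually".
- **Stopping rule (7.7.3).** The main criterion is qualitative. One limb is near-certain evidence that "one treatment regimen is clearly indicated or contraindicated in terms of a net difference in therapeutic effect"; the other is evidence likely to change routine practice. The number attached to both is: "Criteria for the above will usually be a difference in CTCAE Version 4 significant at p<0.001".
- **Primary endpoint (6.2.1).** "Change at 12 months in the bowel disease subset of the Modified IBDQ Quality of Life questionnaire". Section 6.3 bases the sample size on it.
- **Status of CTCAE (6.2.2 and 6.4).** Physician grading on the modified CTCAE form is secondary endpoint iv. After the Fisher tests for bleeding and faecal incontinence, section 6.4 says: "There will be no formal statistical analysis of the other secondary endpoints". Changes in CTCAE grade come first in the list of descriptive analyses that follows.
- **The form (Appendix 4).** It has sixteen named disorders and one row for others. Each is graded separately, and no total score is defined.
- **Toxicity monitoring (6.5).** The share of patients reaching grade 3 or 4 and the highest grade are compared between arms for safety. Section 6.5 does not link this to the stopping rule.

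**The concern.** The rule covers benefit as well as harm, because it speaks of a regimen being indicated or contraindicated. A trial powered on a patient-reported bowel score therefore has, as its only numerical guide for stopping on efficacy, a clinician-graded outcome that the final analysis will merely describe. An IDMC that followed the guide could recommend stopping for benefit on CTCAE before IBDQ-B had its planned information, leaving the primary question underpowered. It would have no agreed threshold for judging a striking IBDQ-B result.

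A CTCAE difference is also not a defined test. With 17 rows graded at several visits and no summary named, two statisticians could compute different p-values from the same data and both claim to be applying the rule. How much protection p<0.001 gives depends on which one is used.

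**Working it through.** **1. Which endpoint the plan is built on.** Section 6.3 gives a difference of 7.5, SD 10, 2:1 allocation, two-sided level 1.67%, 85% power and 99 evaluable patients (66:33).

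- Noncentrality = 7.5 / (10 × √(1/33 + 1/66)) = 7.5 / 2.132 = 3.518.
- With the noncentral t on 97 degrees of freedom, power is 85.8%. At 96 patients (64:32) it is 84.6%. The smallest 2:1 total reaching 85% is 99, as stated.
- Recruitment: 99 / 0.85 = 116.5, so 117, as stated.
- Level: 3 × 1.67% = 5.01%, the stated 5% across IBDQ-B, bleeding and incontinence.

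The design figures reproduce, and CTCAE grading as listed (secondary endpoint iv) has no share of the 5%.

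**2. What p<0.001 means on CTCAE.** Section 7.7.3 gives no figure to reproduce, so the result depends on the reading.

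- *One summary fixed in advance:* two-sided false-positive chance 0.1% per look.
- *Any of the 17 rows may trigger (an assumption):* upper bound 17 × 0.001 = 1.70% per look. If rows are independent, 1 − 0.999^17 = 1.69%.
- *The same with correlated rows:* a simulation of 17 equicorrelated normal statistics (400,000 replicates) gives the following.

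| Assumed correlation | Chance per look |
|---|---|
| 0.3 | 1.6% |
| 0.5 | 1.3% |
| 0.8 | 0.8% |

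These figures combine false benefit with false harm. Taking the two directions as equally likely, false benefit alone is about half, so at most about 0.85% per look.

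**3. What the same threshold would cost on IBDQ-B.** Take p<0.001 at each interim and 1.67% at the final test. The number and spacing of looks are assumptions, since the protocol fixes neither. Simulation (4,000,000 replicates) gives the following.

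| Looks (information fraction) | Type I error on IBDQ-B |
|---|---|
| One (1/2) | 1.72% |
| Two (1/3, 2/3) | 1.76% |
| Three (1/4, 1/2, 3/4) | 1.79% |

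Adding the other two endpoints, the total is 1.72 + 2 × 1.67 = 5.06% to 1.79 + 2 × 1.67 = 5.13%, against 5.01% now.

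**4. How often the IBDQ-B threshold would be crossed.** Under the planned effect the chance at information fraction t is Φ(3.518√t − 3.291).

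- t = 21/99: about 5%.
- t = 1/2: about 21%.
- t = 3/4: about 40%.

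The threshold would seldom stop the trial early, as intended for a guard of this type.

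**The case against.** The best defence is that the CTCAE line is not a boundary. It says what the criterion will usually be, for a committee that reports recommendations to the TSC and TMG, and the governing test is qualitative. The IDMC oversees interim efficacy, sees IBDQ by arm and may request more. **This stands.** A reader might infer that the primary endpoint has no stopping criterion at all, or that the IDMC would have to carry on despite decisive IBDQ-B evidence. The text supports neither. What is missing is a numerical criterion for IBDQ-B.

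A reader might also multiply the any-row figure over looks and conclude that the rule carries a 5% or larger chance of a false stop: 3 × 1.70% = 5.1% for three looks. That needs any single row to count, and it simply sums over looks that share patients. The protocol does not state the any-row reading, and its insistence on a net difference points away from it. Sparse rows may also be unable to reach the threshold. With 21 patients assumed split 14:7, an item present in five patients, all on placebo, gives Fisher p = 21/20349 = 0.00103. Nor does a CTCAE look spend any of the 1.67%.

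Section 1.2 says "Physician assessments appear to under-report morbidity", which might be taken to discredit CTCAE here. Its example is RTOG grading in prostate trials, and equal under-reporting in both arms would tend to make a CTCAE trigger harder to reach. It adds little.

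Section 6.4 governs reporting of secondary endpoints and does not forbid monitoring tests, and section 6.5 plans some for safety. That is fair, but 6.5 supplies neither the p-value in 7.7.3 nor any rule for benefit.

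Finally, the visit, test and number of looks may be set in an SAP or IDMC charter that is not shown. Their absence is not the point. The protocol does name an endpoint for its numerical criterion, and a charter that moved the criterion to IBDQ-B would depart from it.

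**Conclusion.** The point holds as a mismatch. The one statistical criterion in 7.7.3 is placed on a descriptive secondary outcome with no defined summary, while the primary and powering endpoint goes to the IDMC without one. This follows from the text alone and needs no multiplicity calculation.

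The size of the multiplicity problem is conditional. Per look it is 0.1% if one CTCAE measure is fixed, at most 1.7% if any row may trigger, and about 0.8% to 1.3% at assumed correlations of 0.8 to 0.5. The any-row reading is neither stated nor excluded.

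It does not follow that CTCAE should be used for harm only. In this trial it also grades the late bowel effects being treated, so it is legitimate supporting evidence on efficacy. The sample size, the level and the final test are unaffected, and the existing rule is discretionary. **Severity: should-fix.**

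**What to change.** Amend 7.7.3 in three respects:

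1. State that the p<0.001 guide (Haybittle-Peto type) for stopping for benefit applies to the between-arm difference in 12-month change in IBDQ-B. The qualitative standard and the IDMC's discretion stay as they are.
2. State that the final IBDQ-B test is at 1.67%. Then either acknowledge the small inflation (about 1.72% to 1.79% for one to three looks, number and timing assumed) or remove it by lowering the final level slightly once the looks are set.
3. Keep CTCAE grades and adverse events in the IDMC report as supporting evidence and for safety review by IDMC judgement, using the two summaries already named in section 6.5: the share of patients at grade 3 or 4, and the maximum grade.

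The cost is a sentence or two in the protocol and the matching text in the IDMC charter. No new data, visits or patients are needed, because IBDQ by arm is already supplied to the IDMC.
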